# Assessment of perceptive accuracy for motor performance in persons with multiple sclerosis

## Introduction

The majority of people with multiple sclerosis (PwMS) have impaired gait and sit-to-stand function: they walk slower, with an increased energetic cost of walking and cluster-specific alterations from the physiological gait pattern, while lower limb extensor weakness and diminished postural control have also an impact on their sit-to-stand performance. (1-4)

After sustained activity these impairments tend to increase for a large part of PwMS: motor performance fatigability, the objectively measured acute performance deterioration, may involve both quantitative and qualitative aspects of their motor performance. (5, 6)

This can be a barrier to participation in leisure-time physical activity (PA), creating a vicious circle leading to increase in disability: inactive PwMS walk slower with an increased energetic cost of walking, consequently experiencing more reductions in walking bouts quality and distance in their daily life.

Furthermore, motor performance impairments and levels of PA, in this population, may also be linked to sensory abnormalities, personal beliefs and fluctuations of symptom intensity. (7-11)

Fatigue is the hallmark symptom in MS, with reported prevalence reaching 78%, and PwMS with higher levels of perceived fatigue tend to become less physically active in their daily life, also in absence of motor performance fatigability. (12, 13)

Generally, fatigue is a sense of tiredness and lack of energy that can interfere with a person's usual daily activities and, leading to increase the weighting of effort costs in cost-benefit evaluations, it can be a functional interoceptive signal to stop or modify our activity, take appropriate rests or pace our efforts. (14)

[figure not shown]

Figure 1 The predictive model of bodily states. Illustration of the interoceptive core control network and of the precision weighted inferential process forming perception. Adapted from (15)

The efficiency of this self-regulation system depends on the ability of the central interoceptive core control network to accurately judge our body state (which resources are available versus necessary to achieve a desired outcome) and, when carrying out physical activity, to timely produce allostasis adjustments (i.e. 'actions to maintain the body in homeostasis') through interactions with the

autonomous nervous system: rebalancing its activity, with a shift from energy saving to energy expenditure. The perception of the body homeostatic state is constantly updated through an inferential process: there is always a self-generated prior prediction confronted with the actual sensory signal, in a precision weighted manner (see Figure 1).

Therefore, potential sustained input signaling a diagnosis of low allostatic performance (i.e. chronic interoceptive surprise= persistent inaccuracy of prior predictions) can give raise to the perception of fatigue as 'lack of control over body states', in this framework located at a metacognitive level. (15-17) During goal-directed motor performance the brain relies on interoceptive, exteroceptive and proprioceptive signals to gauge the ongoing performance: all these sensory signals have to be integrated and, with multiple sclerosis, this process can be affected by the neuropathology and the prior beliefs may therefore dominate the perception, lowering their perceptive accuracy.

It can become harder for some PwMS to adapt to new experiences, with the risk of maladaptive changes in the way they carry out daily life activities and in the participation in physical activity: possibly hypoactivity due to underestimation of true physical capacity, or hyperactivity in the opposite case. (18, 19)

Keeping in account that perception (and its accuracy) may vary in time, for different body-parts and for different activities, it is important to have an holistic and task-relevant approach to its assessment. In this view, perception is a multifaceted ability which can be studied at different levels, forming separate dimensions:

- Accuracy, degree of truthfulness of perception compared to performance
- Attention, degree of attention for perceptive cues
- Sensibility, self-beliefs over one's own perceptive accuracy and attention
- Awareness, correspondence between measured (objective) and reported (subjective) dimensions

These dimensions can be quantified specifically, with different methods and for different organ systems ('body axis'), in various experimental tasks of perceptual discrimination or correspondence. (20-22)

[figure not shown]

Figure 2 Framework of perceptive abilities assessment. In the present study we will measure objective and subjective perceptive accuracy for motor task-performance. Adapted from (Murphy et al., 2019)

The aim of this study is to characterize perceptive abilities in PwMS compared to controls when performing prolonged functional tasks such as walking and repeated standing from a seated position.

## Methodology

### Participants

44 PwMS and 44 healthy controls (40, +10% to cover possible dropouts and missing data) will be recruited from the Flemish MS rehabilitation centers in Melsbroek (NMSC) and Pelt (Noorderhart RMSC), and as well from the REVAL research center in UHasselt and its established network (eg. UMSC Patient Platform). Information flyers will be distributed in the centers and online content via the website and social media of REVAL and the Flemish MS society; no economical compensation will be provided by the research organization to the participants of this study. We will search age and sex-matching subjects for the healthy controls, considering a 5-year range per subject. After giving informed consent, demographics of age and gender, height and weight, years of education, as well as MS-related information such as EDSS, type of MS, use of assistive device for walking in daily life, and years since diagnosis, will be collected and provided by the centers or via self-report. The participants will be instructed to keep their normal routine but to avoid extraneous physical activity at least 24 hours before the data collection session.

- Inclusion criteria for PwMS: age between 18 and 65 years old; a diagnosis of MS (2017 revisions of the McDonalds criteria); ability to walk for 6 minutes without rest and without the need of a walking aid; ability to repeatedly perform the sit to stand transitions on a standard chair (43cm seat height) without hand support. Additionally, no relapses >1 month preceding the start of the study.
- Inclusion criteria for healthy controls: age between 18 and 70 years old, sex- and age-matched on a group level.
- Exclusion criteria: cognitive impairment hindering understanding of study instructions, pregnancy, and musculoskeletal disorders in the lower limbs (not related to MS), cardiovascular red flags for exercise (screened with Physical Activity Readiness Questionnaire), other diagnosis for neurological or metabolic disease limiting the full execution of the tests (eg. peripheral neuropathy altering the foot plantar sensibility).

Inclusion/exclusion criteria will be controlled at the beginning of the first session: the participant will read the criteria presented in the informed consent and will be asked to confirm that he/she can enroll in the study.

[figure not shown]
In particular cardiovascular red flags for increase in physical activity will be screened with the Physical Activity Readiness Questionnaire, a self-assessment tool including 7 questions. In case of a positive response to one of the questions the participant will be directed to consult his/her physician before enrolling in the study.

Finally, in case of a female participant unsure about her pregnancy state we will offer a free pregnancy test to control for it before enrolling in the study.

[figure not shown]
### Experiment outline

This is an exploratory observational study with experimental tasks to measure perceptive accuracy for motor performance in people with multiple sclerosis and healthy matched controls. This study proposes primary and secondary research questions which will be tested in the context of two different motor tasks, namely walking and sit to stand, and will be performed in two or three days: in case the participant could complete the questionnaires at home, via the provided web service (Castor®) the first and second sessions can be efficiently merged in one, reducing time demand and travelling costs for the participant. The first day (Clinical assessment and familiarization) serves to

obtain a characterization of participants, and it will include familiarization sessions, to ensure that the participants understand the instructions and can cope with all the motor and perceptive tasks. On the second day (Part A) the self-paced performance variations protocols will be performed twice, with adapted instructions (detect the qualitative or quantitative aspects of motor performance) and counterbalanced order, for each the two studied motor tasks: walking (Task 1) and sit to stand (Task 2). On the third day (Part B) the experimentally-induced performance variations protocols will be performed for the two studied motor tasks. The study flows with the clinical assessment + familiarization session, parts A and B can be seen in the next page, presented in Figure 3.

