#### Part A- Perception of self-paced performance variations (2 hour and 30 minutes)

## Part B- Perception of imposed performance variations (1 hour and 40 minutes)

[figure not shown]

Figure 3 Experimental outline of the study. \*Note that Clinical assessment + Familiarization and Part A can be also on the same day. VAS-F= Visual analogic scale for fatigue, COP= Center of pressure

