#### 6.4 Rate of Perceived Stability \*

Afterwards, the participants will perform the 6 Minute Walk Test (6MWT), walking back and forth in a 30m corridor as fast and safe as possible for 6 minutes, the 30 seconds Chair Stand Test (30CST), repeating STS transitions as fast and safe as possible for 30 seconds, and the Dual Joint Position Test (DJPT), a test for proprioception. (25)

Except for the T25FW, the participant will wear wearable sensors in pre-defined body positions for the gait and STS tests (6 OPALs – APDM technology© IMU sensors: 2 over the dorsal part of the feet, 2 on the lower legs, 1 anterior to the sternum and 1 posterior to the third/fourth lumbar vertebra; 1 Polar H10 chest-band for real-time heart rate monitor).

Figure 4 Wearable sensors placement on the body and working prototype of the force sensing device for perceptive tasks

The perceived fatigue will be asked just before and immediately after the 6MWT and the 30CST using the VAS-F, a 0-10 visual analogical scale for state fatigue.

Figure 5 10 points visual analogic scale for fatigue (VAS-F)

- **Familiarization with motor and perceptive tasks**

At this point the participant will be familiarized with the experimental procedures and the experimenter is defining the ranges of performance variations that will be experimentally-induced in part B. This will happen in the presented order:

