#### **Range of imposed performance variations (part B) – Treadmill walking**

A treadmill familiarization procedure will ensure that every participant is enrollable to perform experimental part B. The subjects will be asked about previous experiences with treadmill training/use and this will be noted down in the participant file: participants will undergo 10 minutes of treadmill walking with the supervision of a physiotherapist to familiarize with the moving belt, position and use of safety bars and other general safety and usability issues.

A speed-range definition procedure will permit the quantification of the appropriate personalized range of experimentally-induced performance variations for every participant. All the participants will start walking on the treadmill at 50% of their *maximal treadmill walking speed* (speed calculated from their overground performance in 6MWT: maximal speed maintained for at least 15 seconds during the test) and they will be asked to confirm if that is their *comfortable treadmill walking speed*; if this is not the case the experimenter will adjust the speed based on the participant's subjective reports and, finally, will let them walking at that constant speed for one minute.

Immediately after the selection of their *comfortable treadmill walking speed* (i.e. during the one minute of constant speed walking) the participants will be instructed to maintain their position on the treadmill, in the antero-posterior direction, adapting their gait to the belt continuous acceleration toward their maximal walking speed (selected from their overground performance in 6MWT, see paragraph above). This speed range, will be used as personalized range of experimentally-induced performance variations (in Part B).

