Participants will be also equipped with noise-cancelling headphones to avoid auditory perception of steps rhythm and influence of possible environmental distractions. Using wearable sensors to detect motor performance (spatiotemporal and kinematic parameter detected with a configuration of 6 OPALS – technology© IMU sensors: 2 over the dorsal part of the feet, 2 on the lower legs, 1 anterior to the sternum and 1 posterior to the third/fourth lumbar vertebra, see figure 4) will allow us to then compare the time and frequency of the reports with the actual speed variations, cutting out the steps executed while turning, and propose novel outcome measures: the change in speed at the first report as a perceptive threshold for overground walking speed changes, informing on the minimal clinically important change, and the ratio between reporting frequency and actual speed variability, reflecting perceptive accuracy (see example plot in Figure 6).

[figure not shown]

Figure 6 Perceptive accuracy for walking speed variations during overground 6MWT: Task 1 illustration, wearables placement and Perception vs Performance plot graphic illustration

The intensity of perceived fatigue will be asked just before and immediately after the test using the VAS-F (see Figure 4). Furthermore, a short structured interview will follow including the following question: "On a scale from 0 to 100, how certain are you that you have been precise/accurate in detecting ongoing variations in your performance? Please mark your confidence level on the presented visual scale". This question is then followed by an open-ended question where the participant is asked to report on which sensory information he/she was relying to gauge performance variations and give the reports: "On which aspects of your motor performance where you paying attention to detect variations and decide to give a report during the task? Please list them here".

[figure not shown]

Figure 7 Visual scale for confidence rating: subjective beliefs on their perceptive accuracy

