## Data and statistical analysis

Motor performance data (gait and STS kinematic, kinetics and spatial-temporal parameters) will be acquired by wearable sensors and extracted from Moveo software (APDM) as .csv file or raw data, and Matlab scripts will be used in case of parameters requiring specific calculation. Data acquired from the participants reports on their perception, during the experimental tasks in Part A and Part B, will be extracted with dedicated Matlab scripts. Statistical analysis will be performed using SPSS (V. 28.01). Tests of normality (Shapiro-Wilk test) will be used to determine if parametric or non-parametric statistical tests have to be used for the comparisons and correlations. The  $\alpha$  for all analyses will be set at 0,05.

**Clinical assessment** outcomes, with a particular focus on the MAIA-2, ISAQ and PAS scores and subscores, will be compared between groups with an independent T test (or with its non-parametric equivalent Mann-Whitney U-Test), to detect significant differences in the subjective beliefs about perceptive abilities.

In the **experimental Part A** we will obtain the participants' minimal perceptive threshold for self-paced performance variations which will be compared between groups with an independent T test (or with its non-parametric equivalent). We will also relate the frequency of the reports with the measured performance variability (coefficient of variation of the selected motor performance parameter: gait speed or STS duration) to obtain a novel outcome measure reflecting perceptive accuracy. We will study it between and within groups using a mixed model ANOVA with time and group as factors to detect significant differences between PwMS and controls and its variations relative to the accumulation of fatigue during the prolonged motor tasks. To investigate its interference with perceptive accuracy the difference between the subjective rate of fatigue (VAS-F) pre-post task protocols will be included in the analysis as covariate.

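### Some participants may do Part A on the same day as the clinical session, and the Part A analyses have no term for session format or for the fatigue carried in

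*Combined protocol and SAP*

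**What the plan says.** **Schedule.** The Experiment outline describes two or three days. It states that "in case the participant could complete the questionnaires at home" through the web service, "the first and second sessions can be efficiently merged in one". The note to Figure 3 repeats the option: "Note that Clinical assessment + Familiarization and Part A can be also on the same day". The Questionnaires section leaves the online-or-paper choice to the participant.

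**What precedes Part A on a merged day.** The clinical session has two fast T25-FW trials and a 6MWT, "walking back and forth in a 30m corridor as fast and safe as possible for 6 minutes". It also has a 30CST, "repeating STS transitions as fast and safe as possible for 30 seconds". In the treadmill familiarization, "participants will undergo 10 minutes of treadmill walking", followed by belt acceleration toward the maximal walking speed.

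**Balancing.** The counterbalancing described for Part A concerns only whether the quantity or the quality pair of tasks comes first.

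**Measurement and model.** For Part A Task 1: "The intensity of perceived fatigue will be asked just before and immediately after the test using the VAS-F". Task 2 follows the same scheme. In Data and statistical analysis, the Part A mixed model ANOVA has time and group as factors, and "the difference between the subjective rate of fatigue (VAS-F) pre-post task protocols will be included in the analysis as covariate". The perceptive threshold is compared between groups by a t test or its non-parametric equivalent, with no covariate.

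**The concern.** Session format is a design variable that differs between participants for a practical reason, is not allocated, and appears in no Part A analysis. Participants on a merged day may begin the perceptive tasks with more fatigue than those who come back on another day. The plan itself treats recent exertion as relevant: the Participants section asks people to avoid unusual physical activity for 24 hours before data collection, and the Introduction says that motor impairments increase after sustained activity in a large part of PwMS.

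The pre-task VAS-F records the level carried in, but the model uses only the difference. What is at stake is the PwMS-HC comparison in Part A. Part of an observed difference in accuracy or threshold could reflect who had been tested earlier that day, or how strongly earlier testing affected each group.

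**Working it through.** **1. The plan's own figure.** The only design number that can be recomputed is the sample size: 40 × 1.10 = 44 per group, as stated. The plan gives no effect size, SD or power, so the 40 cannot be checked. The point does not depend on it; 40 per group is used below as the analysed number.

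**2. What the covariate carries.** A participant going from 2 to 4 on the VAS-F and one going from 6 to 8 both have a covariate value of 2. The starting level is therefore not in the model, although it is collected.

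**3. When merging biases the group difference.** Let p1 and p0 be the merged shares in PwMS and HC, and d1 and d0 the effects of merging on the outcome in SD units. The spurious group difference is p1·d1 − p0·d0.

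- Equal shares and equal effects: zero; merging only adds variance.
- Equal effects d: (p1 − p0)·d.
- Equal shares p: p·(d1 − d0). For example, 0.5 × (0.8 − 0.3) = 0.25 SD.

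The documents give none of these quantities, so the values below are assumptions.

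**4. Size with equal effects and no true group difference.** With 40 per group the standard error is √(2/40) = 0.224 SD. The two-sided false-positive rate (sidedness assumed) at bias b is 1 − Φ(1.96 − b/0.224) + Φ(−1.96 − b/0.224).

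| Difference in merged share | Effect of merging (SD) | Spurious difference (SD) | False-positive rate |
|---|---|---|---|
| 0 | 0.3 to 0.8 | 0 | 5.0% |
| 25 points | 0.3 | 0.25 × 0.3 = 0.075 | 6.3% |
| 25 points | 0.5 | 0.25 × 0.5 = 0.125 | 8.6% |
| 25 points | 0.8 | 0.25 × 0.8 = 0.20 | 14.5% |
| 50 points | 0.3 | 0.50 × 0.3 = 0.15 | 10.3% |
| 50 points | 0.5 | 0.50 × 0.5 = 0.25 | 20.1% |
| 50 points | 0.8 | 0.50 × 0.8 = 0.40 | 43.2% |

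**5. Does the planned covariate help?** A simulation (3000 runs per scenario, one outcome per participant, no true group effect) assumed the following: 25% merged in one group; pre-task VAS-F with mean 3 and SD 1.5, raised 2 points by merging; a rise during the task with mean 2 and SD 1.5; values limited to 0–10; accuracy falling 0.3 residual SD per point of pre-task VAS-F. The false-positive rates were:

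| Imbalance | No covariate | VAS-F change | Pre-task VAS-F | Session format |
|---|---|---|---|---|
| none | 5.5% | 5.3% | 5.2% | 5.5% |
| 25 points | 8.4% | 8.3% | 4.8% | 5.1% |
| 50 points | 21.5% | 21.2% | 4.9% | 5.0% |

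Under these assumptions the change score removes essentially none of the bias, while either of the other two terms removes it. Accuracy was made to depend on the starting level, so this shows the mechanism and does not estimate what will happen in this study.

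**The case against.** **The change score is the right covariate for its question.** The Part A research questions ask whether differences are modulated by fatigue accumulating over the protocol, and the pre-post difference measures exactly that. This stands. A reader might infer that the change score is a mistake and should be replaced by the fatigue level; the documents do not support that. What remains is that the same model also carries the group comparison, for which accumulation alone does not account for the level carried in. How weakly a change score predicts the fatigue level is no measure of bias in that comparison, so no such figure is used here.

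**Bias is not shown.** The documents give no merged share and no sign of imbalance, and the questionnaire choice is offered to everyone without distinguishing groups. This also stands. The bias is conditional.

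**The earlier load may be modest.** A reader might infer that merged participants arrive exhausted. The documents do not say so: the tests are limited by safety, eligible PwMS can walk 6 minutes without rest, and the treadmill part is a supervised familiarization. Figure 3 is not shown and may contain rest periods. Part A is allotted 150 minutes for about 24 minutes of task time (2 × 6 minutes of walking plus 2 × 36 repetitions × 10 s = 12 + 12), so there is room for rest. Rest would reduce the effect of merging without making the two formats the same.

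**Pre-task fatigue may be part of the MS effect.** The Part A hypotheses expect lower accuracy in PwMS with higher reported fatigue. Adjusting for pre-task VAS-F in the main model could remove part of the contrast under study. This is a good reason to keep it to a sensitivity analysis. It does not apply in the same way to session format, which is a matter of scheduling.

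**Part B.** A reader might extend the point to Part B, whose model also uses the VAS-F change. Part B is held on its own day, so the merging argument gives no ground for changing it.

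**Conclusion.** The point holds in a limited form. Session format varies by participant circumstance, is not balanced by group in the readable text, and enters no Part A analysis. The one fatigue covariate does not carry the starting level, and the threshold comparison has no covariate at all. Carried-in fatigue is thus measured but not adjusted for.

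The group difference is biased only if the merged share or the effect of merging differs between groups; otherwise the cost is mainly extra variance. The size cannot be known from the documents. The illustrations run from no bias to 0.40 SD, the latter needing a 50-point imbalance and a 0.8 SD effect, neither of which the documents indicate. In an exploratory observational study this calls for a cheap safeguard in the analysis; it does not show that the Part A results will be wrong.

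**What to change.** - Record session format (merged or separate day), which should be derivable from visit dates, and tabulate it by group.
- Include session format as a term in the Part A mixed models.
- Give the Part A threshold comparison a model-based version with group and session format.
- Keep the pre-post VAS-F difference as the accumulation covariate. Add a sensitivity analysis that also includes pre-task VAS-F, and report results with and without it, saying that pre-task fatigue may be part of the MS effect.
- A single session-format term corrects for unequal shares but not for an unequal effect of merging. Describing the group difference separately by format would show the latter, if numbers allow.

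**Cost:** SAP wording, one extra model term (one degree of freedom), one table and one extra analysis. No new assessment is needed. The readable text does not list session format as a recorded variable, so it has to be named as one.
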